#### • Instruments:

- 1) Costs of the two types of setting ("Fast track" and classic) will be compared taking into account hospitalization and ambulatory costs which will be obtained via the patient EDS number as discussed with the medico-information department ([name]). In addition, home care will be accounted for via invoices and family/friends loss of earnings will be calculated based on the number of absent working days. With Switzerland's median wage of CHF 6118 per month in 2012 and approximately 21 working days per month, we can estimate a median wage of CHF 291 per working day.
- 2) Patients satisfaction in both groups will be evaluated via a satisfaction questionnaire on their day of return home and at their follow-up visit one month after surgery.
- 3) Patients will be given a logbook questioning them on their pain awareness, their digestion and their mobilisation during their hospital stay.
- 4) Morbidity during the first month post-operation (i.e. readmission rate, number of infections and number of thromboembolic events) will be evaluated via the medical staff case report form.

A medical staff case report form containing their detailed clinical pathway will be used to verify patient's adhesion rate at each stage of the protocol.

A care map for each group will be used by the medical staff as a synopsis of the clinical pathway and will have to be signed by each medical intervener (nurse, gynaecologist and anaesthetist).

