**Hypothesis and objectives:** 

Hypothesis:

The concept of "Fast track" which has proven its effectiveness in colorectal surgery is applicable in

gynaecological surgery.

Perioperative "Fast track" setting is more efficient than conventional setting in laparoscopic

hysterectomy for benign indication.

Objectives:

The main objective of this study is to evaluate effectiveness of the "Fast track" concept in

laparoscopic hysterectomy for benign indication in comparison to conventional setting in terms of

cost and patient satisfaction. Earlier rehabilitation, diminution in hospitalization length and stable

postoperative morbidity (number of thromboembolic events, number of infections, readmission

rate) will be verified.

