**Methods:** 

Design:

Randomized control trial: the randomization in two groups will be performed by computer using

block of different sizes (2 and 4) before patient inclusion. Sealed, opaque and numbered

envelopes will be prepared and patients will be included consecutively.

Population:

All patients in our gynaecology department, in whom an indication of total or subtotal

laparoscopic hysterectomy for benign indication with or without adnexectomy has been

established (including robot-assisted interventions), will be proposed this study.

Exclusion criteria:

Patients needing an additional surgical procedure such as a prolapse surgery or urinary

incontinence surgery as well as malignant pathologies will not be included in the study due to

prolonged operative time which could compromise early home return. Non-French speaking

patients will also be excluded from the study due to the necessity of their collaboration in filling a

logbook drawn up in French on a daily basis during their hospitalization.

6

Etude CCER n° 15-103 : Fast Track\_V.2.0-2015.09.29

« Fast track » surgery on patient undergoing minimally invasive gynaecologic procedure: a randomized clinical trial. V2.0 – 2015.09.29

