#### Preoperative strategy:

- Hospitalization on surgery day
- No prolonged fasting (solids stopped 6 hours before surgery and liquids encouraged up to two hours before surgery)

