#### Postoperative strategy:

- o Pain control using balanced analgesia
- o Gum chewing
- o Antithrombotic prophylaxis by low-molecular-weight heparin (40mg/60mg, depending on patient weight, 6 hours post-op during entire hospital stay)
- Early oral refeeding (as of 4 h postoperative)
- Rapid mobilization (as of 4 h postoperative)
- Venflon removal 6 hours post-op
- o Standard criteria for hospital discharge the day after surgery, checked by a physician:
  - Lack of organ dysfunction (evaluated by physical examination)
  - > Afebrile condition
  - Simple effective analgesia
  - Normal feeding
  - Independent mobility
  - Patient consent
- o Planned outpatient follow-up: stitches/ skin staples removal on day 7, postoperative checkup on day 30
- o Home care if needed

The protocol will have to be well-known by surgeons, anaesthetists and the nursing team.

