#### Secondary:

- Patient satisfaction (2)
- ➤ Earlier rehabilitation (3): pain comparison via pain scale (0-10) and resumption of normal bowel function via day of first stools and gas post-op
- Morbidity during the first post-operation month (4):
  - -readmission rate
  - -number of infections
  - -number of thromboembolic events

In order to measure the impact of the intervention on our practice, the length of hospitalization "Fast track" and conventional setting will be compared.

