#### Ethics:

The study protocol will be submitted to the ethics committee of the Geneva University hospital (HUG). If approval is given by the ethics committee, all patients with a surgical indication of laparoscopic hysterectomy for benign indication in the gynaecology department of the HUG will be proposed to participate in this study. Eligible patients will receive oral and written information by a research nurse. Study participation will be voluntary and participants will be free to withdraw from the study at any time. Written consent will be given before inclusion in the study.

To ensure patient confidentiality, once a patient accepts to participate in the study she will receive a study number on a first-come, first-served basis. For instance [name], 58th participant will be known under patient 58 irrelevant of whether she has been attributed to the protocol FT or conventional. This number will be written on the patient information and consent form, the medical staff case report, the care map and the patient's log-book. The document containing the name of the patient paired with her study number (la main courante) will be kept under lock at the clinical research unit of the gynaecology department. Only the investigators and the research nurses will have access to this document.

The patient information and consent form, the medical staff case report, the care map and the patient's log-book will also be kept at the clinical research unit of the gynaecology department where only the investigators and the research nurses will have access.

Study participation presents no particular risk for patients since the "Fast track" concept has already demonstrated efficiency in colorectal surgery with no morbidity increase. Moreover, the various stages of the "Fast track" protocol are already commonly applied on a case-by-case basis in our current conventional setting. The choice to exclude from the study patients needing an additional surgical procedure such as a prolapse surgery or urinary incontinence surgery as well as malignant pathologies is justified by the fact that operating time is prolonged which could compromise homogeneity of the sample. Non-French speaking patients will also be excluded from the study due to the necessity of their collaboration in filling a logbook drawn up in French on a daily basis during their hospitalization.

[figure not shown]

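### Day of first stools and gas is recorded only in an in-hospital logbook, although both arms may go home the day after surgery, so dates after discharge have no stated route into the data

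*Combined protocol and SAP*

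**What the plan says.** The combined protocol and SAP lists earlier rehabilitation among the secondary outcomes (Issues, Secondary) and measures it by "pain comparison via pain scale (0-10) and resumption of normal bowel function via day of first stools and gas post-op". The matching entry, Instruments item 3, reads: "Patients will be given a logbook questioning them on their pain awareness, their digestion and their mobilisation during their hospital stay". The exclusion criteria under Methods describe the same form as a "logbook drawn up in French on a daily basis during their hospitalization", and the Ethics section gives the same limit. The logbook is thus tied to the hospital stay in three places.

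Both arms have the entry "Hospitalization on surgery day" under Preoperative strategy and "Standard criteria for hospital discharge the day after surgery, checked by a physician" under Postoperative strategy. The six discharge criteria are the same in both arms. They include normal feeding but not the passage of gas or stools.

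Outpatient contacts are planned on days 7 and 30 in both arms, with no bowel question stated for either. Under Instruments, the one-month questionnaire covers satisfaction, and the case report form covers morbidity and adherence to the pathway. Type of analysis names methods for cost, satisfaction and morbidity. It gives none for first stools or gas, and no rule for a patient who leaves before either has occurred. Length of stay is itself compared between arms, and the Objectives expect it to fall, without saying by how much.

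**The concern.** The period in which a first stool or first gas can be recorded is the length of stay. A patient who meets the discharge criteria first leaves no date. Two consequences follow, and they should be kept apart.

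- **Loss of data.** With short stays in both arms, many first-stool dates may never be collected, and no analysis can recover them.
- **Unequal windows.** If the conventional arm stays longer, later events are seen only in that arm. A comparison restricted to recorded days would then make the shorter-stay arm look faster even with no true difference.

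At stake is the bowel-function part of earlier rehabilitation, one of the two measures that the Issues section gives for that outcome.

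**Working it through.** **The plan's own figure.** The sample size rests on cost: a difference of 0.5 SD, two-sided 5%, power 90%. Per arm, 2 × (1.960 + 1.282)² / 0.5² ≈ 84.1, rounded up to 85, so 170 in total. The figure is reproduced, and it does not depend on bowel outcomes.

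**Inputs for the bowel outcome.** From the documents: 170 patients, 1:1, two-sided 5%, discharge possible on the day after surgery. Assumed, because the documents give no event times: time T to first stools is lognormal with median 1 to 3 days and log-SD 0.5; stay S is gamma with mean 1 or 2 days and SD 0.3 day; T and S are independent; the hazard ratio is 1.5.

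**Share unrecorded.** For the hospital logbook this is P(T > S), obtained by simulation. For a fixed window to day 7 it is 1 − Φ[(ln 7 − ln median)/0.5]. With median 3 that is 1 − Φ(0.847/0.5) = 1 − Φ(1.69) ≈ 4.5%.

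**Approximate power.** With D = 170 × (1 − share unrecorded) events, power ≈ Φ(√D × ln 1.5 / 2 − 1.96) = Φ(0.203√D − 1.96). Example: median 1 day and 1-day stay give D = 170 × 0.47 ≈ 80, and Φ(1.81 − 1.96) ≈ 44%.

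| Median to first stools | 1-day stay: unrecorded / power | 2-day stay: unrecorded / power | Day-7 window: unrecorded / power |
|---|---|---|---|
| 1 day | 53% / 44% | 10% / 71% | under 0.1% / 75% |
| 1.5 days | 78% / 24% | 30% / 60% | 0.1% / 75% |
| 2 days | 90% / 13% | 51% / 46% | 0.6% / 75% |
| 3 days | 98% / 6% | 79% / 23% | 4.5% / 73% |

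The day-7 column assumes that every home page comes back.

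**Another shape.** With exponential times and a fixed stay, the share unrecorded is exp(−ln 2 × stay/median). For medians of 1 to 3 days this is 50–79% at 1 day and 25–63% at 2 days. The size changes with the model, but the loss does not disappear.

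**First gas.** With assumed medians of 0.5 to 0.75 day, 13–34% is unrecorded at a 1-day stay (power 58–69%) and 0.4–3% at a 2-day stay.

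**Unequal stays, no true effect.** Take mean stays of 1 and 1.8 days. The 1.8 is the low end of the conventional laparoscopic stays in Figure 2 of the protocol; the 1 is assumed. Mean recorded days of first stools are then 0.88 v 1.19 (median 1.5) and 0.98 v 1.34 (median 2). The spurious gap is about 0.31 to 0.35 day in favour of the shorter stay. With equal stays the gap is 0.

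**The case against.** The strongest reply is that every magnitude is assumed. The documents give no time to first stools, and the discharge entry sets criteria for leaving on day 1 without saying that most patients will. The only laparoscopic stays cited are 1.8 to 3.9 days, under conventional care. This stands. A reader might infer that first stools will be known for only a minority, or that a real effect will be missed; the documents do not support either as a general statement. At a 2-day stay and a median of 1 day, about 90% of dates are recorded. First gas, the other half of the measure, holds up better.

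A reader might also infer that the planned bowel comparison is biased towards Fast track. The plan names no bowel analysis, and admission day and discharge criteria are the same in both arms. Bias needs both unequal stays and an analysis of recorded days alone. Heaviest loss in both arms and large bias also belong to different scenarios: the first needs short stays in both arms, the second a longer stay in one.

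Nor does the point extend to pain. The logbook is filled in daily, so scores on common early days can be obtained, and nothing in the plan proposes averaging pain over the stay.

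Finally, neither the logbook nor the case report form is reproduced, so a bowel item after discharge cannot be excluded. But the text limits the logbook to hospitalization three times and states no other source. Censoring at discharge would use the partial data, but it assumes that discharge is unrelated to bowel recovery. That is uncertain, because discharge requires normal feeding.

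**Conclusion.** The point holds as a gap in data collection with a cheap remedy. As written, a first stool or first gas after discharge has no stated route to be recorded. For first stools, under a lognormal model with medians of 1 to 3 days, the share unrecorded is about 53–98% at 1-day stays and 10–79% at 2-day stays, against at most about 5% to day 7 with full return. Power for an assumed hazard ratio of 1.5 is about 6–44%, 23–71% and 73–75% respectively. These ranges show how much could be at stake; they do not predict what this trial will lose. A bias in favour of the shorter-stay arm arises only if stays differ, which the plan expects without giving a size, and only if recorded days alone are compared. The effect is confined to one component of a secondary outcome.

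**What to change.** In both arms, continue only the first-gas and first-stool items to the same fixed postoperative day regardless of discharge, for example day 7. Collect the page at the day-7 or one-month contact, both already planned; day 7 leaves less to recall. State in Type of analysis that both outcomes are analysed as time from surgery, censored at the end of that window or at the last entry if earlier. If the actual logbook already continues at home, correct the three statements in Exclusion criteria, Instruments and Ethics to say so, and add the analysis.

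The cost is one home page with two simple items, some non-return and some late recall. Non-return reduces the gain: with an assumed 15–30% missing and almost no loss otherwise, D is 170 × 0.85 ≈ 145 to 170 × 0.70 = 119, and power about 68% to 60%. No new visit, no change in discharge criteria and no change in sample size are needed.

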#### Sample size

Sample size is calculated based on the difference of means for total costs in between the two groups including hospitalization costs and costs during the first month after surgery (ambulatory, home care and social environments loss of earnings). The null hypothesis tested will be that costs are identical in the two groups.

In order to obtain a power of 90% for type I error with a significance threshold at 0.05 in a two-tailed distribution and in order to highlight a difference equal to 0.5 standard deviations which is clinically relevant, the study will need to include 170 patients (n1 = 85; n2 = 85). Assuming an average cost of CHF 10'000 per hysterectomy for benign indication (CHF 12'809 in 2013, information given by [name], financial medical controller), it will be possible to highlight a statistically significant difference of CHF 1400 per surgery corresponding to 10% of the total amount which would be considered as clinically relevant.

### Type of analysis

The two groups will be compared in terms of their background characteristics which could influence study outcome. Factors such as age, BMI, hypertension, diabetes, and smoking will be taken into consideration. Patients adhesion rate at each stage of the protocol in the 'Fast track' group will also be evaluated. Special attention will be given to hospitalization length in the two groups.

Data will be analysed by the intention-to-treat approach. Patients will remain in the group to which they were initially allocated to at the beginning of the study.

Total average costs between the two groups will be compared using a T-Test with a 95% confidence interval. In the same way, global and per intervention patient satisfaction will be analysed with a T-Test even though they do not follow a normal distribution (right-tailed distribution). A second total average cost analysis will also be performed excluding patients who presented major perioperative complications requiring for instance intensive care unit which may influence study outcome with no direct relation to "Fast track" protocol.

Readmission rate, number of infections and number of thromboembolic events will also be compared between the two groups in terms of risk differences with a confidence interval of 95%. If these complications are sufficiently numerous, a Fisher's test will be used for comparison.

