**Recruitment:** 

During pre-hospitalisation visit where surgical indications are established, eligible patients will

meet a research nurse who will explain the study giving patients oral and written information. If

the patient agrees to participate in the study, she will be included randomly in one of the two

groups after having signed a consent form. She will immediately be informed of her allocation to

the "Fast track" or the control group in order to best prepare her personal perioperative planning.

To increase the number of patients recruited, patients that meet the criteria of the study but who

were not informed during the pre-hospitalisation visit will be contacted by a research nurse after

the weekly colloquium of surgical indications, colloquium where all surgical indications of the

department of gynaecology of the HUG are confirmed.

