**Intervention:** 

Two types of perioperative settings will be compared:

o Group 1: "Fast track" protocol

Group 2: conventional setting

1) "FAST TRACK" protocol

Preoperative evaluation and information:

o Patient information of the study during the pre-hospitalisation visit and patient consent to

participate in the study prior to hospitalization.

o Patient general health state optimization proposal prior to hospitalization:

Smoking cessation, if necessary (specialized consultation)

Weight loss, if necessary (nutrition consultation)

Patient autonomy and social environment evaluation (home care proposal if

necessary)

7

« Fast track » surgery on patient undergoing minimally invasive gynaecologic procedure : a randomized clinical trial. V2.0 – 2015.09.29

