# 2) «Conventional setting» protocol

#### Pre-hospital assessment

o Surgical indication determination and surgical procedure explanation

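### No pre-allocation pain score is mentioned, so the secondary pain comparison stays unbiased but gives up precision that one question at consent could supply

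*Combined protocol and SAP*

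**What the plan says.** All references are to the combined protocol and SAP.

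- **Pain outcome.** The secondary issues list pain on a 0-10 scale as one component of earlier rehabilitation.
- **Pain instrument.** Instruments, item 3: "Patients will be given a logbook questioning them on their pain awareness, their digestion and their mobilisation during their hospital stay". The exclusion criteria under Methods describe it as a "logbook drawn up in French on a daily basis during their hospitalization".
- **Start of the stay.** The preoperative strategy is the same in both arms: "Hospitalization on surgery day".
- **Allocation.** Under Recruitment, if "the patient agrees to participate in the study, she will be included randomly in one of the two" groups, and she is told at once which one. This happens before admission.
- **Background characteristics.** Type of analysis: "Factors such as age, BMI, hypertension, diabetes, and smoking will be taken into consideration". The section gives neither a time of recording nor a form. It also names no analysis for pain.
- **Steps between allocation and admission.** The Fast track protocol under Intervention offers smoking-cessation and nutrition consultations before admission, where needed. The pre-hospital assessment of the conventional arm lists only this: "Surgical indication determination and surgical procedure explanation".

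**The concern.** Women having a hysterectomy for benign disease may differ in the pain they already have. If part of the variation in post-operative pain reflects pain before surgery, a comparison that ignores it carries noise that a single earlier question could remove. Balance in prior pain between the arms could not be shown either. The score cannot be recovered later: one not taken before the envelope is opened is lost.

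There is a smaller, related gap. BMI and smoking are to be compared as background characteristics, and between allocation and admission one arm is offered help with both. A background table should therefore rest on values taken before allocation, and the plan does not say that it will.

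**Working it through.** **1. The plan's own figure.** Inputs from Sample size: difference 0.5 SD, two-sided 0.05, power 90%.

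n per arm = 2 × (1.960 + 1.282)² / 0.5² = 84.1, rounded up to 85, so 170 in total. This reproduces the stated size. Power at 85 per arm is 90.3% by the normal approximation (90.0% with the t distribution). The figure concerns total costs; the documents give none for pain.

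**2. When pain could first be scored.** The sequence in the text is consent, allocation and disclosure, then (in the Fast track arm) the consultations, then admission on the day of surgery, with the logbook kept from there. Any logbook entry, even one made before the operation, follows open allocation.

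**3. What a baseline score would gain.** Let r be the correlation between the pre-allocation and the post-operative score. In a linear model with arm and baseline score, the variance of the arm difference is multiplied by 1 − r², and the confidence interval width by √(1 − r²). The equivalent number per arm is 85/(1 − r²). The difference detectable with 90% power is 3.242 × √(2/85) × √(1 − r²), in SDs of post-operative pain. The values of r, and the 0.4 SD pain difference in the last column, are assumptions.

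| r | Variance lower by | CI width lower by | Equivalent n per arm | Detectable difference (SD) | Power for 0.4 SD |
|---|---|---|---|---|---|
| 0 (unadjusted) | 0% | 0% | 85 | 0.497 | 74.1% |
| 0.1 | 1% | 0.5% | 86 | 0.495 | 74.6% |
| 0.3 | 9% | 4.6% | 93 | 0.474 | 78.0% |
| 0.5 | 25% | 13.4% | 113 | 0.431 | 85.3% |

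The factor 1 − r² leaves out the small cost of estimating one slope, so at r = 0.1 there is practically no gain.

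**4. How large a chance imbalance could be.** Assume a baseline pain SD of 2.5 points. The standard error of the difference between arms is 2.5 × √(2/85) = 0.383, and 1.96 × 0.383 = 0.75 points. That is the 95% chance limit, which about 5% of trials would exceed, and not a typical imbalance. With equal SDs at both times, it carries into post-operative pain as r × 0.75: 0.23 points at r = 0.3 and 0.38 at r = 0.5. The ordinary standard error of the unadjusted comparison already allows for this.

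**5. BMI and smoking.** No arithmetic is possible: the documents give neither uptake of the consultations nor the interval between allocation and surgery.

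**The case against.** The strongest reply is that nothing here is invalid. Randomisation protects the unadjusted comparison, pain is one part of one secondary outcome, and the primary test is untouched. All of this stands. A reader might infer that missing baseline pain biases the comparison; it does not. The cost is precision, and it is small if r is 0.3 or less.

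A second reply is that the logbook and case report form are not among the documents and may hold a pre-operative item. That is possible, so the supportable statement is that none is mentioned. A logbook entry on the day of surgery would still follow open allocation.

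A reader might also infer that the background table will be post-treatment in one arm, and that using BMI and smoking would then remove part of the Fast track effect. The documents support neither step:

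- No section says these values are taken at admission. The pre-hospitalisation visit under Recruitment is an earlier contact, before allocation, in both arms.
- The consultations are proposals made where needed, so smoking and weight must already be known in that arm when they are offered.
- Ethics notes that Fast track steps are already used case by case in conventional care, so the contrast between arms may be modest.
- Type of analysis names a t-test, risk differences and Fisher's test, and no covariate-adjusted model. Without adjustment nothing is removed from the effect.

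Finally, the plan names no pain analysis at all, and that gap comes before any choice of covariate. This is fair, and the fix has to cover it: collecting the score gains nothing unless the analysis uses it.

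**Conclusion.** The point holds as an inexpensive improvement to a secondary outcome. As written, pain is scored only after open allocation and no earlier score is mentioned. The consequence is lost precision, not bias: about 1% to 25% of the variance for r between 0.1 and 0.5, or 0.5% to 13.4% of the confidence interval width. Both r and the 2.5-point SD used for the imbalance figure are assumptions.

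For BMI and smoking, the documents leave the recording time unstated and do not show it to be late. That part is a request for clarification and no more. Neither part affects the primary cost comparison or the sample size of 170.

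**What to change.** - **Recruitment and Instruments.** Have the research nurse record a 0-10 pelvic/abdominal pain score after consent and before the envelope is opened, in both arms. For a patient contacted after the weekly colloquium and not seen in person, ask by telephone.
- **Type of analysis, pain.** Compare post-operative pain with a linear model containing arm and the baseline score, and name the logbook entry or entries that form the outcome.
- **Type of analysis, background table.** Record BMI and smoking at the same contact and state that the group comparison uses these pre-allocation values. If the existing forms already capture them before allocation, one sentence saying so is enough.

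The cost is one or two extra questions at a contact that already takes place, one line on the case report form and a short addition to the analysis text. There is no extra visit, and the primary analysis and the 170 patients stay as they are.

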#### • Issues:

#### o Main:

> Total costs: hospitalization costs and costs during the first month after surgery (ambulatory, home care and family/friends loss of earnings) (1)

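### The primary cost comparison is valid but unadjusted: prespecifying a short list of baseline covariates would use information the plan already treats as relevant and settle how it enters the analysis

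*Combined protocol and SAP*

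**What the plan says.** The main outcome is "Total costs: hospitalization costs and costs during the first month after surgery". Under Type of analysis, the primary test is: "Total average costs between the two groups will be compared using a T-Test with a 95% confidence interval". No regression, covariance or stratified analysis appears anywhere in the document. The one further cost analysis leaves out patients with major perioperative complications; it is not covariate-adjusted.

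On baseline factors the same section says: "The two groups will be compared in terms of their background characteristics which could influence study outcome". It continues: "Factors such as age, BMI, hypertension, diabetes, and smoking will be taken into consideration". It does not say whether this means a descriptive table, an adjustment, or both.

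The Methods section (Population) admits total and subtotal "laparoscopic hysterectomy for benign indication with or without adnexectomy has been" "established (including robot-assisted interventions), will be proposed this study". The Design paragraph describes computer randomization in blocks of 2 and 4 and names no stratification factor. Surgical route is not among the five listed baseline factors.

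**The concern.** Total cost may vary with patient risk and with the planned procedure. In an unadjusted comparison, all of that variation stays in the error term. If some of it can be predicted from facts known before randomization, a model that includes those facts gives a narrower interval from the same 170 patients. The Ethics section excludes additional procedures partly to keep the sample homogeneous, so procedure mix is already regarded as relevant. The mix that remains is handled in neither the randomization nor the analysis.

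The second issue is specification. Saying that factors will be considered, without saying how, leaves room to choose covariates once the data are known. The Recruitment section has each patient told her arm at once, so the trial is open-label. In that setting a fixed, written analysis matters more. This part of the point does not depend on how well the factors predict cost.

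**Working it through.** **Inputs from the Sample size section.** Two-sided alpha 0.05, power 90%, difference 0.5 SD, 85 per arm. The quoted detectable difference of CHF 1400, set equal to 0.5 SD, implies an SD of 1400 / 0.5 = CHF 2800.

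**The plan's own figure.** A two-sample t-test at 0.5 SD with 85 per arm has noncentrality 0.5 × √(85/2) = 3.26 on 168 degrees of freedom, which gives power 0.8999. The stated 170 reproduces and already assumes no adjustment.

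**Inputs that are assumed.** The documents give no R² of any factor with cost, no share of robot-assisted cases and no cost by route. R² is therefore varied from 0 to 0.3.

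**Effect of adjustment.** With N = 170 and k covariates:
- Residual variance falls by the factor (1 − R²).
- Estimating the covariates costs about (N − 3)/(N − 3 − k). This is 167/164 = 1.018 for k = 3 and 167/159 = 1.050 for k = 8.
- The standard error relative to the t-test is √[(1 − R²) × that factor].
- Power uses noncentrality 3.26 divided by this ratio, on 168 − k degrees of freedom.

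Example, k = 3 and R² = 0.1: ratio √(0.9 × 1.018) = 0.957, noncentrality 3.26 / 0.957 = 3.40, power 92.3%.

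| Assumed R² | Power, 3 covariates | CI width vs t-test | Power, 8 covariates |
|---|---|---|---|
| 0 | 89.5% | about 1% wider | 88.5% |
| 0.05 | 90.9% | about 2% narrower | 90.0% |
| 0.1 | 92.3% | about 4% narrower | 91.5% |
| 0.2 | 94.9% | about 10% narrower | 94.2% |
| 0.3 | 97.0% | about 16% narrower | 96.6% |

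The eight-covariate column stands for the five listed factors plus route, total or subtotal, and adnexectomy. Break-even R² is k/(N − 3): 3/167 = 0.018 for three covariates and 8/167 = 0.048 for eight. At the same R² the shorter list does better, and it risks less if the covariates predict little.

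**Chance imbalance in route.** With robot share p and cost gap D, the imbalance contributes an SD of D × √(2p(1 − p)/85) to the arm difference. Assume p = 0.2 and D = CHF 2000: the SD is CHF 123, and route alone explains 0.2 × 0.8 × 2000² / 2800² = 0.08 of the cost variance. The standard error of the unadjusted difference is 2800 × √(2/85) = CHF 430, and the CHF 123 is already inside it. Removing it gives √(430² − 123²) = CHF 412. This is the same gain as in the table, seen from another side, and must not be added to it.

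**The case against.** The strongest reply is that nothing is broken. Randomization makes the t-test valid, the difference in mean cost is the right quantity for a cost question, and the sample was sized for exactly this unadjusted test. All of that stands.

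A reader might infer more than the documents support, in four ways:
- **That the trial is wasting precision by a known amount.** No R² is given, and the text says only that the factors could influence outcome. They are not shown to predict cost. Below an R² of about 0.02 for three covariates, or about 0.05 for eight, adjustment gains nothing.
- **That imbalance in robot-assisted cases biases the result.** The unadjusted estimate is unbiased over randomization, and its interval already reflects such imbalance.
- **That the plan intends to inspect baseline differences first and then choose covariates.** No such sequence is stated. The most natural reading is that the five factors will fill a baseline table. Later adjustment is left open, not announced.
- **That heterogeneity was ignored.** Prolapse, incontinence and malignant cases are excluded, which narrows it.

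One practical objection also stands. No section says that planned route is written down before randomization. The arm is revealed at once, and indications are confirmed at a weekly meeting that may come later. Adding route therefore needs a new item on a form as well as new wording.

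**Conclusion.** The point holds as an inexpensive improvement and a gap in specification. It does not show an error in the test or in the 170-patient sample size. With three covariates, the change in power at 0.5 SD runs from a loss of about half a percentage point at R² = 0 to a gain of about 7 points at R² = 0.3. The interval runs from about 1% wider to about 16% narrower. These figures assume 85 analysed patients per arm, a linear model and an R² that the documents do not supply. They are a range, not a forecast. The case for stating in advance how baseline factors enter the analysis holds whatever the R².

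**What to change.** In Type of analysis, name as the primary analysis a linear regression of total cost on arm plus a short fixed covariate list, for example age, BMI and planned route (robot-assisted or not). Report the adjusted difference in mean cost with a robust 95% confidence interval, in all patients as randomized. Report the unadjusted t-test alongside as a sensitivity analysis. State that the remaining listed factors are for description only, so that no further adjustment is left open.

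Use values recorded before randomization and do not update them. The Fast track arm includes weight-loss and smoking-cessation consultations before admission, so later values of BMI or smoking could be affected by the arm. The route could also change once the arm is known. Record the route intended at that moment, and keep it in the analysis even if the weekly meeting or the operation changes it.

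The cost is a few sentences and one item on the form, completed before the arm is revealed. No extra patients or visits are needed. The downside is a negligible loss of precision if the covariates turn out not to predict cost.
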